## Photobiomodulation in ASD

- GAF
- CTAE
- Concomitant Medications
- ADHD-SC
- BRIEF-A/P

### During study visits:

- A study doctor will ask the participant questions about the participant's ASD symptoms and general health. The study doctor will also ask if the participant is having any side effects, and if they have taken any other medications during the previous week (see Table I for details).
- We will ask the participant to fill out five questionnaires at baseline (beginning of Week 1) and midpoint (end of Week 4) and this will take approximately 30 minutes. We will ask participant to fill out one questionnaire on beginning of weeks 3, and 6 (approximately 5-10 minutes). We will ask participant to fill out six questionnaires at endpoint (approximately 40 minutes). For children under the age of 18, we will ask their parent/guardian to complete these forms.
- Optional: If a parent/caregiver is available, we will ask them to complete three observer- & self-rated measures on the REDCAP at baseline and endpoint. The observer-rated MGH Social Emotional Competence Scale (MGH-SECS-I) will also be administered at midpoint. Aside from the observer-rated MGH-SECS-I, any measures that were completed during the screening visit (week 99) will only be completed again at endpoint.

For quality control purposes, assessments completed during these visits may be recorded. These recordings will be used to monitor quality control and inter-rater reliability in this study. Each recording will be coded with subject initials and an identification number to maintain confidentiality. These recordings will be stored in a password-protected database or on an encrypted external hard drive stored in a locked filing cabinet in a secure office.

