At the baseline visit, the subject will be examined via a video call to inspect the sites of application (left and right forehead) for any possible skin lesions (e.g. laceration or signs of inflammation) which would contraindicate the treatment. The subject will then be instructed on appropriate administration of tPBM. The treatment device is classified as an “Exempt” device in accordance with the requirements of the international standard EN 62471 – Photobiological safety of lamps and lamp systems and, when used correctly, the output is less than the maximum permissible exposure (MPE) no special controls are needed for the environment it is to be used in. At the time of study implementation, the staff will be provided training on basic safety procedures relative to the use of the device. The staff will then instruct the subject on the administration of the tPBM with careful observation that the subject appropriately places the headband device. For subjects ages 9-17, the delivery of the tPBM is expected to last 10-40 minutes total (simultaneous application on the left and right forehead). The subject will be asked to rest for five minutes after the delivery of tPBM. Sites of application will be inspected at each study visit. Subjects will be instructed to administer the treatment sessions daily for eight weeks, with each session lasting 10-40 minutes. Subjects will be instructed to contact the investigator or a member of his staff at any time between visits concerning adverse events or worsening of symptoms. Subjects ages 18-59 will be instructed to administer the treatment sessions daily for eight weeks, with each session lasting 20-50 minutes. Subjects will be instructed to contact the investigator or a member of his staff at any time between visits concerning adverse events or worsening of symptoms.

The following assessments will be performed at the Baseline Visit:

- CGIs

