### **8. ASSESSMENTS (See Table I for an assessment schedule)**

Subjects will be evaluated at biweekly intervals. At each weekly visit, measures of safety and efficacy will be obtained using assessments of psychiatric symptoms and functioning (CGIs, GAF) and measures of adverse effects (CTAE). Additionally, height and weight will be collected during the screening evaluation (week 99) and the final study visit (week 8 or endpoint).-At the midpoint (end of week 4) and final study visits (Week 8 or Endpoint), additional clinician- and subject-rated assessments will be repeated (see below for details). Optional observer-rated assessments will be completed at the baseline (week 1) and final study visits.

All data will be collected and entered into REDCap. REDCap is an electronic data capture system that streamlines data collection and ensures data integrity. REDCap software allows researchers to design and implement study surveys electronically for collecting, storing, retrieving, and manipulating data. Participants will be sent the RedCap link via encrypted email. The link will not allow the participant to access any other data stored on the password-protected database. Only those subjects who receive the link via email will be able to access the questionnaires. The responses will then be transmitted securely via an encrypted connection and stored in a secured database. Electronic data capture eliminates the need for subsequent data entry by staff, thus minimizing human error. However, in the event that REDCap is

malfunctioning, study staff will print all study instruments and study data will be collected in paper form.

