### **Subject-Rated Behavioral Measures (or Parent/Guardian rated if the subject is <18 years of age)**

*(Administered at screening evaluation)*

- Demographic Interview: This brief interview will collect information regarding socioeconomic status and history of head injury or trauma [27].

*(Administered at baseline, midpoint, and final study visits)*

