### **Observer-Rated Behavioral Measures (or Parent/Guardian rated if the subject is <18 years of age)**

*(Administered at baseline and endpoint)*

- Social Responsiveness Scale-Second Edition Informant-Report (SRS-2; [28]): a 65-item rating scale completed by parents/caregivers that is used to measure the severity of autism spectrum symptoms of the subjects as they occur in natural settings.
- Adult Behavior Checklist (ABCL; [32]): An observer-rated assessment of maladaptive behavioral and emotional problems, social competence and substance use in adults ages 18-59.
- Child Behavior Checklist (CBCL): A parent-rated assessment of maladaptive behavioral and emotional problems, social competence, and substance use in children.

*(Administered at baseline, midpoint, and endpoint)*

- MGH Social-Emotional Competence Scale [Informant-Rated Measure] (MGH-SECS-I): This is a 37-item scale that assesses change in the frequency and severity of core and associated symptoms of ASD.

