**Table I. Study Schema**

Weeks	99	0	1	2	3	4	6	8
tPBM Device Subject Training	X	X						
tPBM Treatment (9-17)- 10 min/day		X						
tPBM Treatment (9-17)- 20 min/day			X					
tPBM Treatment (9-17)- 30 min/day				X				
tPBM Treatment (9-17)- 40 min/day					X	X	X	X
tPBM Treatment (18-59)- 20 min/day		X						
tPBM Treatment (18-59)- 30 min/day			X					
tPBM Treatment (18-59)- 40 min/day				X				
tPBM Treatment (18-59)- 50 min/day					X	X	X	X
Diagnostic Assessments								
MGH-ASD-SCL	X							
Psychiatric Evaluation & Medical History	X							
Physiological Procedures								
Physical Examination	X							X
Urine pregnancy test (females only)	X							X
Vital Signs (Height & weight)	X							X
Clinician-Rated Assessments								
MGH-SECS-C		X				X		X
CGIs	X	X		X		X	X	X
GAF	X	X		X		X	X	X
HAM-A	X					X		X
HAM-D	X					X		X
AISRS	X					X		X
CTAE		X		X		X	X	X
Concomitant Medications	X	X		X		X	X	X
Progress Note	X	X		X		X	X	X
Patient-Rated Assessments								
Demographic Interview	X							
ASRS (18+)		X				X		X
SRS-2 (Self/Informant)	X	X				X		X
BRIEF-A/P		X				X		X

Photobiomodulation in ASD

Q-LES-Q		X				X		X
TSRQ				X			X	
MGH-SECS-I (Observer)	X	X				X		X
ABCL/CBCL	X	X						X

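### The caregiver bullet and the assessment schedule disagree on whether an informant SRS-2 done at screening is repeated at baseline, and Section 9 does not say which score is the before value

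*Combined protocol and SAP*

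**What the plan says.** Under During study visits in Section 7, the optional caregiver bullet first asks for three measures at baseline and endpoint. It then says that, apart from the MGH-SECS-I, "any measures that were completed during the screening visit (week 99) will only be completed again at endpoint". The Screening Process paragraph lets an available caregiver complete one to three observer-rated measures at week 99. The informant SRS-2 is on Section 8's observer-rated list.

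Section 8 schedules the same forms without that restriction: "Optional observer-rated assessments will be completed at the baseline (week 1) and final study visits". Its observer-rated list puts the informant SRS-2 and the ABCL or CBCL under "Administered at baseline and endpoint". Table I has one row, "SRS-2 (Self/Informant)", marked at weeks 99, 0, 4 and 8. The ABCL/CBCL row is marked at weeks 99, 0 and 8.

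Section 7 makes change from baseline on self- and/or observer-rated SRS-2 part of the primary outcome. Section 9 compares a pre-treatment baseline with the last assessment, in pairs. Section 6.A requires an SRS raw score of at least 85 and names no rater.

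**The concern.** Staff cannot follow both schedules for a caregiver who completed the informant SRS-2 at screening. Under the Section 7 bullet, that participant has informant scores at weeks 99 and 8 only. Under Section 8 and Table I there is also a week-0 score. Section 9 does not resolve this, because a week-99 score and a week-0 score both precede treatment.

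Caregiver forms at screening are optional and vary in number, so observer-rated change could use a screening baseline for some participants and a week-0 baseline for others. The design has one arm and an entry threshold on the same scale. If the score that admitted a participant is also the baseline, regression to the mean is counted as improvement, with no control group to remove it.

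**Working it through.** The plan gives no power or bias figure to reproduce, so the check is a comparison of texts followed by a calculation for scale.

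**Texts side by side**

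| Source | Observer forms before treatment |
|---|---|
| Section 7, caregiver bullet | Not repeated at baseline if done at week 99, except MGH-SECS-I |
| Section 8, opening paragraph and observer-rated list | Baseline |
| Table I, SRS-2 row | Weeks 99 and 0 |
| Table I, ABCL/CBCL row | Weeks 99 and 0 |

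The SRS-2 row is the weaker evidence. It merges self and informant forms, and it marks week 4, when Section 8 does not schedule the informant form. The ABCL/CBCL row covers instruments that Section 8 describes as observer- or parent-rated, so it shows the clash more cleanly.

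**Who is affected**

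- Ages 9-17: the preceding bullet asks for "five questionnaires at baseline (beginning of Week 1) and midpoint (end of Week 4)" and adds "For children under the age of 18, we will ask their parent/guardian to complete these forms". Section 8's subject-rated list, parent-rated under 18, includes the SRS-2 under "Administered at baseline, midpoint, and final study visits". Both point to a parent score at week 0.
- Adults: the non-optional screening SRS-2 is completed by the participant, which points to entry on self-report. Self-report is scheduled again at baseline. The informant form is the one exposed to the no-repeat rule.

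**Size.** From the documents: cut-off 85 (Section 6.A) and up to 20 exposed (Section 4). Assumed: normal scores, SD 25, pre-selection mean 95 (80 to 105), same-rater retest correlation r = 0.8 (0.7 to 0.9), self-informant correlation c = 0.5 (0.3 to 0.7), no true change, a two-sided 5% Wilcoxon test, and 5 or 10 of 20 affected.

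The mean excess of the selecting score is h = SD × φ(a) / (1 − Φ(a)), with a = (84.5 − mean) / SD to allow for rounding.

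- Mean 95: a = −0.42, h = 25 × 0.3653 / 0.6628 = 13.78
- Mean 80: a = 0.18, h = 22.90
- Mean 105: a = −0.82, h = 8.98

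*Adult selected on self-report, informant screening score as informant baseline.* With independent rater errors, self-report at screening correlates c with the informant at screening and c at endpoint, so the bias is (c − c) × h = 0. With shared visit-to-visit fluctuation it is c × (1 − r) × h.

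- Middle: 0.5 × 0.2 × 13.78 = 1.38 points
- Range: 0.3 × 0.1 × 8.98 = 0.27 to 0.7 × 0.3 × 22.90 = 4.81

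*Same rater decides entry and supplies the baseline.* The bias is (1 − r) × h.

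- Middle: 0.2 × 13.78 = 2.76 points
- Range: 0.1 × 8.98 = 0.90 to 0.3 × 22.90 = 6.87

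**Simulated rejection under no change** (10,000 trials in middle cases, 8,000 in extremes)

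| Case | 5 of 20 affected | 10 of 20 affected |
|---|---|---|
| Adult, shared fluctuation, middle | 4.7% | 5.5% |
| Adult, extreme (mean 80, r 0.7, c 0.7) | 5.5% | 7.9% |
| Same rater, middle | 5.2% | 6.3% |
| Same rater, extreme (mean 80, r 0.7) | 6.0% | 11.5% |

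With nobody affected the rate is 4.9%. The standard error of a difference between two runs is √(2 × 0.05 × 0.95 / 10,000) = 0.3 percentage points, so the two middle cases with 5 affected cannot be told from none. Repeat runs moved the middle figures by less than one percentage point.

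If observer-rated SRS-2 is analysed alone in 10 participants, all affected, rejection is 5.2% in the adult case and 7.3% in the same-rater case, against 4.4% with a week-0 baseline. In the same-rater middle case, false 30% responders are 2.4% instead of 1.4% of those affected, or 10 × (0.024 − 0.014) = 0.1 person per 10.

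**The case against.** The strongest reply is that the Section 7 sentence is a deliberate, specific rule: a form done at screening serves as baseline and spares the caregiver a repeat. Section 7 avoids redundant burden in the same way for diagnostic data. That reading is possible, but neither Section 8 nor Table I carries it, and Section 9 does not adopt the screening score as baseline. The need for a baseline rule stands on either reading.

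The second reply is that few participants are exposed and the central results are near nominal. This largely stands and limits the size of the point. It is also fair that the self- and/or observer-rated wording leaves the informant score's weight in the primary outcome open.

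A reader might infer more than the documents support:

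- *That the whole primary SRS-2 result rests on the selecting score.* The provisions for youths and for adult self-report both point to week-0 scores. CGI-ASD-Improvement, also primary, is not scored from the SRS-2.
- *That no SRS-2 is taken at baseline, because the list introduced by "The following assessments will be performed at the Baseline Visit" omits it.* That list also omits the MGH-SECS-C, ASRS and Q-LES-Q, which Table I marks at week 0, so it settles nothing.
- *That about 11% is a ceiling on the error rate.* It is the same-rater middle case with all 20 affected. At mean 80 and r 0.7 that scenario gives roughly 34% to 36%. All 20 being affected is implausible here.

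**Conclusion.** The point holds as a minor to moderate one. The schedules conflict, and Section 9 lacks a rule for the before value of observer-rated SRS-2. The main exposure is adults whose informant completed the form at screening. For them, spurious improvement is between nil and about 1.4 points in the middle case, with 4.8 at the edge of the assumed range. The larger same-rater figure needs one rater to both decide entry and supply the baseline. For youths, that would require reading the caregiver bullet as overriding the parent-form provisions. For adults, it would require entry to be decided on the informant score.

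The number affected, the SD, the mean and the correlations are all assumptions. The case for acting rests on the contradiction and the undefined baseline of a primary component, and does not need a large bias.

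**What to change.** 1. Section 7, During study visits: extend the MGH-SECS-I exemption to the informant SRS-2, so that it is completed at week 0, and bring this bullet, Section 8 and Table I into agreement.
2. Section 9, add: For each rater, the SRS-2 baseline is the week-0 score before the first tPBM session, paired with the same rater's endpoint score; the screening score is used only if the week-0 form is missing, and the analysis is repeated without those participants.
3. Section 6.A: state, by age group, which rater's SRS score decides entry.
4. Apply the rule and sensitivity analysis in item 2 to participants already treated, since Section 1 describes the study as ongoing.

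The cost is wording plus one short repeat caregiver form. The observed change may look slightly smaller. Week-0 forms not collected from past participants cannot be recovered, so the sensitivity analysis will lose some of a small sample.

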### **Study Discontinuation**

We will encourage subjects to continue enrollment in the study via follow-up visits regardless of discontinuation of the tPBM. At the end of the study, we will refer the subjects to their counselor and/or psychiatrist at MGH, and will communicate clinical data upon signed authorization. If the CGI-S increases more than 2 points during the study, the subject will be counseled to start or change to an FDA-approved medication treatment. If the CGI-S increases more than 5 points or if a subject becomes actively suicidal as per clinician judgment, termination from the study will be mandated. If a subject is deemed actively suicidal and is believed to be in imminent danger, the study staff will follow a crisis management plan: keep the subject on the phone and alert a clinician. When the clinician comes to the phone they will assess the situation and determine the appropriate next steps. If the subject is appropriate for outpatient monitoring, the subject will be followed with frequent appointments outside the study. Each subject will have the Investigator's contact information as well as instructions on how to call for emergency services, if needed.

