## Photobiomodulation in ASD

A participant may withdraw consent at any time for any reason (e.g., lack of efficacy, adverse events, etc.). A subject may be withdrawn from the study at any time if any of the following conditions are met:

- Worsening of ASD or current/emergent major psychiatric disorder.
- Subjects who experience intolerable adverse effects as determined by the PI.
- Emergent suicidality
- Pregnancy
- Failure to keep study appointments for more than 2 consecutive visits
- Clinical judgment of the investigator

Those subjects who terminate study participation before the completion of the study will be asked to complete all tasks scheduled to take place on the final study visit at the time of study discontinuation.

Subjects may receive three clinical follow-up visits at the completion of the study (or if they are required to discontinue for safety reasons), allowing adequate time for appropriate psychiatric referrals to treaters in their communities. Follow-up visits are optional and are at no cost to participants. These visits are not part of the clinical trial and no research data will be collected during follow-up. Subjects who fail to keep study appointments, or are non-compliant may be dropped from the study. These study subjects will be given a referral to treaters in their area but will not be offered three follow-up visits.

If a subject would like us to forward their clinical history to his/her primary care physician, or a new clinician, we will forward any pertinent information with the proper completed release of information authorization form. If a subject who has come from the clinic of the investigator happens to drop out of the study, he or she will return to his or her treating physician.

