### **Clinician-Rated Safety Measures**

*(Administered at baseline, all treatment visits and at final visit)*

- Clinician-Rated Treatment Emergent Adverse Events Log (CTAE): to record any spontaneous adverse health events experienced during the study, along with duration, severity, cause, treatment, and outcome.
- Concomitant Medications: to record additional medications taken during the study.

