#### **Study Treatment**

Safety will be monitored through treatment-emergent adverse events. Subjects will be monitored for adverse events at each visit. All adverse events will be recorded. A subject may be dropped from the study or dosage may be decreased at any time due to adverse events. All adverse events will be reported to the PHRC according to PHRC guidelines. All concomitant medications will be assessed at every study visit.

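### Intolerable adverse effects can end study participation, and scheduled adverse event collection then stops at the drop visit

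*Combined protocol and SAP*

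**What the plan says.** Section 7, Study Discontinuation, opens with the intention to keep people in the study after they stop the device: "We will encourage subjects to continue enrollment in the study via follow-up visits regardless of discontinuation of the tPBM".

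The list that follows in the same section gives grounds on which a subject may be withdrawn from the study, not merely from the device. One is "Subjects who experience intolerable adverse effects as determined by the PI". Section 10, Study Treatment, agrees: "A subject may be dropped from the study or dosage may be decreased at any time due to adverse events".

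People who end participation early "will be asked to complete all tasks scheduled to take place on the final study visit at the time of study discontinuation". Table I puts the CTAE, the CGIs and the SRS-2 at that final visit.

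On what follows, section 7 says "Subjects may receive three clinical follow-up visits at the completion of the study (or if they are required to discontinue for safety reasons"), and of those visits "These visits are not part of the clinical trial and no research data will be collected during follow-up". The opening part of section 10 offers three months of open treatment after withdrawal for adverse events and attaches no assessment to it.

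Adverse event collection is tied to visits. Section 10 says "Subjects will be monitored for adverse events at each visit". Section 8, Clinician-Rated Safety Measures, gives the CTAE schedule as "Administered at baseline, all treatment visits and at final visit" and has the log record each event's duration, severity, cause, treatment and outcome.

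**The concern.** Safety and tolerability is a secondary objective (section 2). In an open-label study that aims to expose up to 20 people, those who cannot tolerate the device are the most informative for it. The withdrawal rules allow exactly these people to be taken out of the study, after which no research contact is scheduled.

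The CTAE asks for duration and outcome. For an event still open at the drop visit, neither field can be completed from a scheduled contact. An event that first appears after the device is stopped would be known only if someone happened to report it.

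Section 12 says that subjects who develop active suicidal ideation, mania or hypomania will be discontinued. For these events, resolution matters as much as onset. The interim experience described in section 1 comes from adults, whereas ages 9-17 are newly added.

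**Working it through.** The plan gives no figure to reproduce here: no dropout rate, power calculation or adverse event window. The check is a reading of the rules followed by a count from Table I.

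**Step 1. Two different events.**

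- *Stops the device, stays enrolled.* The first sentence of Study Discontinuation applies. There is no drop visit, because final-visit tasks are triggered by ending study participation. Table I lists the CTAE with no condition that the subject still be on treatment. If Table I continues to apply, no visits are lost.
- *Leaves the study for intolerability or safety.* The withdrawal list in section 7 and the drop rule in section 10 apply. Final-visit tasks are done at that time. Afterwards there are only off-trial clinical visits and open treatment, neither with a research assessment.

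The gap lies in the second event.

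**Step 2. What a leaver forgoes.** Inputs: Table I marks the CTAE and CGIs after baseline at weeks 2, 4, 6 and 8, which is 4 visits. Treatment lasts 8 weeks. Section 4 plans up to 20 exposed, so full scheduled observation is 20 × 8 = 160 participant-weeks. Assumption: the drop visit is completed when the person leaves. Weeks lost = 8 − week of leaving; share = weeks lost / 160.

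| Leaves at week | Table I CTAE visits forgone | Weeks without scheduled collection | Share of 160 participant-weeks |
|---|---|---|---|
| 1 | 2, 4, 6, 8 (4 of 4) | 8 − 1 = 7 | 7/160 = 4.4% |
| 2 | 4, 6, 8 (3 of 4) | 8 − 2 = 6 | 6/160 = 3.75% |
| 3 | 4, 6, 8 (3 of 4) | 8 − 3 = 5 | 5/160 = 3.1% |
| 4 | 6, 8 (2 of 4) | 8 − 4 = 4 | 4/160 = 2.5% |
| 6 | 8 (1 of 4) | 8 − 6 = 2 | 2/160 = 1.25% |

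Sections 3 and 8 also mention weekly assessment. The count uses Table I; the weeks-lost column does not depend on that choice.

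**Step 3. What is not lost.** The drop visit supplies a CTAE, the CGIs and an SRS-2, so the event that led to leaving is recorded and an efficacy endpoint normally exists. Section 9 uses the last assessment, at completion or drop visit, and so already accommodates these people.

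**Step 4. Ambiguous terms.** Follow-up visits appear at the start of Study Discontinuation as the means of staying enrolled, and later in the same section as optional visits outside the trial. One visit cannot be both. Separately, section 8 ties the CTAE to treatment visits, which leaves it unclear whether an off-device visit counts.

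**The case against.** A reader might infer that everyone who stops tPBM drops out of data collection, on the ground that the later description of follow-up visits defines the earlier one. The documents do not support this. The later text concerns clinical visits after completion or required safety discontinuation, meant to allow time for referral. The earlier text concerns remaining enrolled. They share a term, and the most natural reading keeps device-stoppers on Table I. What remains for that group is unclear wording.

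A reader might also infer that the causal adverse event goes unrecorded, or that the efficacy result is biased by a known amount. Neither follows. The drop visit includes the CTAE, section 10 requires all adverse events to be recorded, and the documents give nothing from which to size a bias.

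Three further objections carry weight:

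- Withdrawal for intolerability is discretionary, so an investigator could already stop the device and keep the person enrolled. True, but the protocol equally permits the opposite and does not state a preference at that point.
- Cases may be few. Section 1 reports 98% adherence and no treatment-limiting side effects at the interim look. That is not a discontinuation rate, however, and it does not cover ages 9-17.
- Replacing the drop-visit efficacy value with an off-device week-8 value would change what section 9 estimates, and could mix in other treatment: section 7 counsels medication after CGI-S worsening, and section 10 offers open treatment. This stands, and it is why the fix leaves the efficacy endpoint where it is.

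The protocol also gives leavers some cover through continuing clinical care, and enrolled subjects are told to report problems between visits. Neither is scheduled research collection.

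**Conclusion.** The point holds for participants withdrawn from the study for intolerability or safety. For them the drop visit is the last scheduled research contact, so later adverse events and the course of unresolved ones have no scheduled collection. Each such person forgoes 1 to 4 of the 4 post-baseline CTAE visits and 2 to 7 weeks of observation when leaving between weeks 6 and 1. With 20 exposed that is 1.25% to 4.4% of scheduled participant-weeks per leaver, all of it from someone who stopped. These figures assume that Table I governs the schedule and that the drop visit takes place. They measure lost observation, not bias.

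For participants who stop the device but remain enrolled, the defect is limited to unclear terms. The effect on the trial is modest, but the change is cheap, serves the protocol's own stated intention and alters a withdrawal rule that bears on a secondary objective, so it should be made.

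**What to change.** 1. In section 7 (Study Discontinuation) and section 10 (Study Treatment), make intolerability a reason to stop tPBM rather than to leave the study. Unless consent is withdrawn or termination is mandated, continue the remaining Table I virtual visits through week 8 with at least the CTAE and CGIs.
2. For mandated safety terminations, allow the outcome of open CTAE events to be recorded, with consent, at the clinical follow-up visits already offered. The present statement that no research data are collected there needs that exception.
3. In section 8, state that the CTAE is administered at off-device visits. Use a different term for the optional clinical visits.
4. Require the final-visit tasks at device stop, and say in section 9 that this assessment is the efficacy endpoint. Otherwise the last-assessment rule would move the endpoint to an off-device week-8 value. Any SRS-2 or CGI obtained off device at week 8 is supplementary.

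Cost: wording in sections 7, 8, 9 and 10, and retention of 1 to 4 already scheduled virtual visits for each person who stops between weeks 6 and 1. Late events may be confounded by other treatment started after tPBM, so concomitant treatment should be read alongside them.
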